8.1.5. Surveillance and Reporting Procedures

All AEs (except for expected) will be reported. Adverse events will be documented during the scheduled visits. For each sign, symptom or adverse event, the following information will be recorded:

- A brief descriptor of the adverse event
- Start and stop dates
- Intensity (mild / moderate / severe)
- Whether the AE was "serious" or not (as defined below)
- Causal association with the intervention assigned (none / doubtful / possibly / probably / very likely)
- Outcome (resolved / resolved with sequelae / improving / still present and unchanged / death)
- Action taken with respect to the intervention (none / intervention temporarily discontinued / medical therapy required / intervention permanently discontinued / other).

Serious adverse events that are deemed unanticipated and related and therefore required to be reported to the IRB will be telephoned, faxed, or emailed *within 48 hours* of ascertainment by the center PI or study coordinator to the local Institutional Review Board. Because a written record of notification is required, telephone notifications must be followed with written documentation that the IRB has been informed. Unanticipated and related SAEs not resolved by the end of the study or that have not resolved upon discontinuation of the subject's participation in the study will be followed by the clinical site until the event resolves, stabilizes or returns to baseline.

9.3. Stopping rules

This study does not involve major risk to participants. The most likely scenario that would indicate a cessation of the study would be failure to recruit participants or implement the study as planned. Nevertheless, in addition to monitoring recruitment and compliance to the study, we also will monitor the rates of injury in our participants. The study investigators will alert the IRB, if a larger than reasonably expected injury rate occurs in the treatment groups. Other issues that are related to the stopping rules include:

- New information – It is unlikely that new information will become available during this study that would result in discontinuing the trial.
- Limits of assumption – It is possible that the value of data analysis will be limited by differences because of study dropouts or missing data. Baseline differences will be analyzed and effects on the power to detect differences in the outcome measures will be evaluated and discussed with the PI, and the NIH Project Officer. Although an excessive number of dropouts could occur, this has not been our past

experience. In CALERIE study (24 weeks), the dropout rate was only 2% (1 out of 36 enrolled). If the dropout rate for the proposed study exceeds 15%, the study coordinator will initiate a meeting with the PI to discuss strategies to increase retention. If the dropout rate exceeds 25%, the safety officer will meet with the study investigators to determine whether or not the study should continue.

- Limit of rules – We acknowledge that circumstances, other than what are listed, may justify stopping the study.

9.4. Confidentiality

The study investigators will treat participant identity with professional standards of confidentiality. Each participant will be assigned an identification number and all participant protected health information/records/questionnaires/data will be coded and identified using these numbers rather than participant names. The coded participant list identifying participants by name will be stored separately from the number coded records/questionnaires/data. All participant records/data will be stored in locked file cabinets. Study results will be reported as group data and/or by participant identification number only. Study results may be presented in publications or at meetings/conferences, however participant identity will not be disclosed. A participant may request their personal health information or their personal study data/results at any time during the study and will be given copies. All volunteers are assured of their confidentiality both verbally and in the informed consent form. The clinical facilities are strictly limited to the staff of the research institution and to research volunteers. This is accomplished by a variety of stringent security measures. All medical records are stored in locked areas. Access to these areas is limited to the clinical support staff, director of the clinical facilities, and the PIs. Electronic data storage is similarly restricted with only the PIs and authorized persons having access to databases containing confidential clinical records, i.e. those containing name OR other identifying information.

10. DATA MANAGEMENT

10.1. Statistical power and sample size

The primary outcome is energy intake during pregnancy. We were able to apply the energy-balance model to

Table 4. Minimum sample size for power at .80 and .90, ratio between groups 1:2

Standard Deviation kcal/d	Mean Difference kcal/d	Power (β)	Group 1 N	Group 2 N
700	541	.90	27	54
700	468	.80	27	54
700	600	.90	22	44
700	520	.80	22	44
700	688	.90	17	34
700	590	.80	17	34

estimate energy intake in previously reported data on energy requirements during pregnancy [82]. The standard deviation of energy intake in the third trimester was conservatively estimated to be 700 kcal/d using Butte’s data on total energy expenditure and energy deposition of fat mass and fat-free mass.

We hypothesize that women who will exceed 2009 IOM recommendations for weight gain during pregnancy, the ‘High Gainers’, will have a larger energy intake than those who will keep their weight gain within IOM guidelines, the ‘Normal Gainers’. Because of the intervention, we predict to have a decrease in the incidence of ‘High Gainers’ from 66% to a rate below 50%. Therefore we predict that the ratio “High Gainers” to “Normal Gainers” will likely be 1:2. Our power/sample size analysis (Table 2) assumed: 1) power ≥ 0.90 , 2) alpha = 0.05, 3) the null hypothesis will be tested against a two-directional alternative, 4) the common standard deviation for energy intake is 700 kcal/d and 5) conservative estimates that the ratio between the two groups, ‘High Gainers’ to ‘Normal Gainers’ is 1:2.

As shown in Table 2, with subject assignment to the 2009 IOM guidelines being 1:2, we require a minimum of 51 subjects, to detect a between group difference of 590 kcal/d with 90% power or 520 kcal/d with 80% power. To allow for early deliveries, the inability to perform MRI in some subjects late pregnancy, due to limitations with the field of view, and that 10% of subjects will gain less weight than recommended; we aim to complete at least 60 subjects.

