2. BACKGROUND AND SIGNIFICANCE

2.1. Definition and prevalence

Currently in the United States, 31.9% of reproductive age women (20-39 years) are estimated to be obese [1] and 8% severely obese [2]. Obesity at conception as well as excess gestational weight gain leads to adverse health outcomes for the mother [3-6] and more alarming, the infant [6-9] that are sustained for decades later.

In an attempt to counteract these trends, the Institute of Medicine (IOM) performed a detailed review of observational data in pregnant women and infants, and defined, within each BMI classification, boundaries for appropriate weight gain during pregnancy [10]. According to the IOM, gestational weight gain in obese women should be limited to 5-9 kg [10]. To be compliant with the gestational weight gain guidelines, the IOM suggests pregnant women receive dietary advice and physical activity counseling throughout pregnancy. Despite these recommendations, recent data in 227,149 obese pregnant women indicate that more than 55% of obese women in the U.S. exceed the IOM guidelines for gestational weight gain [11]. Furthermore, to date, lifestyle interventions specifically designed to attenuate weight gain in obese pregnant women have failed [12-17]. In order to improve weight management in obese pregnant women, there is a critical need to understand the determinants of gestational weight gain. In support of this contention, the IOM recognized that, "there remains a lack of information to relate dietary intake or physical activity to gestational weight gain even though they are primary determinants of weight gain in non-pregnant individuals" [10].

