There is little knowledge of the determinants of gestational weight gain in pregnant women and no studies have been conducted specifically in pregnant women who are obese. Successful weight management programs in non-pregnant individuals rely on individualized prescriptions of energy intake and physical activity [18-21]. Understanding how changes in energy intake, energy expenditure and physical activity during pregnancy contribute to gestational weight gain is critical for designing effective interventions for pregnant women. To advance the management of gestational weight gain in obese pregnant women, studies are thereby needed to: 1) understand the simultaneous changes in energy intake, energy expenditure and physical activity throughout pregnancy and, 2) evaluate these measures in relation to gestational weight gain and the 2009 IOM guidelines for weight gain during pregnancy.

Objective assessments of energy intake can be derived from the energy balance method by summing total daily energy expenditure and changes in body energy stores. We have shown that the energy balance method can be

used to estimate energy intake during weight loss with good accuracy and precision [22, 23] and have preliminary data validating this method during weight gain. Objective assessments of energy intake have not been undertaken in obese pregnant women and almost no data exist. Using data from a landmark study that collected simultaneous measurements of body composition (by the 4-compartment model) and energy expenditure by the doubly labeled water technique [24], we computed energy intake in the 3rd trimester by the energy balance method. In overweight women with gestational weight gain above the 2009 IOM guidelines ('High Gainers'), energy intake in the third trimester was 3503 ± 666 kcal/d compared to 2617 ± 400 kcal/d for women with appropriate gestational weight gain ('Normal Gainers'). As expected, energy expenditure in these women increased in proportion to gestational weight gain. When the change in energy expenditure was adjusted for change in maternal body weight and body composition (mother plus fetus), energy expenditure was higher than expected but not different between 'High Gainers' and 'Normal Gainers'. These preliminary data indicate that a large energy intake and not an impaired increase in the energy expenditure underlie excess gestational weight gain in 'High Gainers'.

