10.2. Data analysis plan

Analyses will be performed in SAS version 9.3 (SAS Institute, Cary, NC). Statistical significance will be set at $p \leq 0.05$.

Aim 1: Mixed models will be used to analyze differences between 'High Gainers' and 'Normal Gainers' with respect to energy intake during pregnancy estimated with the energy balance method. Adjustments for covariates, such as maternal age, fetal size and parity will be made if appropriate. Least square means will be compared with the mixed models contrasts. Energy intake from the energy balance model will be analyzed analogously in the context of repeated measurements. We expect that energy intake by the two methods will all be significantly higher in 'High Gainers' versus 'Normal Gainers'. In addition, the two methods for measuring energy intake will be cross validated with each other and compared with Bland-Altman analysis. Regression analyses will be used to assess the relationship between energy intake during pregnancy and postpartum weight loss after 1 year. We predict that lower energy intake during pregnancy is associated with better postpartum weight loss results after 1 year.

Aim 2: Analysis of covariance will be used to assess significance of differential changes ('High Gainers' versus 'Normal Gainers') in absolute energy expenditure. Differential changes in energy expenditure after adjustment for changes in maternal and fetal size will be tested analogously. For secondary hypotheses, change in energy expenditure attributable to accelerometer-measured physical activity (steps per min) will be analyzed to investigate its role in differential energy balance in 'High Gainers' versus 'Normal Gainers'.

Analyses of exploratory aims: The change in determinants of energy intake and energy expenditure in blood and urine from early to late pregnancy and 12 months postpartum will be analyzed by repeated measures with IOM classification and time interactions. Adjustments for covariates, such as maternal age, fetal size, parity and early pregnancy values will be made if appropriate. To control for type I error, statistical significance for all multiple comparisons will be adjusted using the Tukey-Kramer method.

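### Aim 1 makes no provision for unequal variances: if one variance is fitted, the preliminary SDs carry over and the predicted 1:2 split occurs, the 5% test runs at about 9.5%

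*Combined protocol and SAP*

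**What the plan says.** Section 10.1 gives the planning spread and where it came from: "The standard deviation of energy intake in the third trimester was conservatively estimated to be 700 kcal/d". It lists the sample-size assumptions, among them that "the common standard deviation for energy intake is 700 kcal/d" and that "the null hypothesis will be tested against a two-directional alternative", at alpha 0.05. On group sizes it says "we predict that the ratio “High Gainers” to “Normal Gainers” will likely be 1:2". Table 4 follows that ratio; its smallest design has 17 and 34 women.

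Section 10.2, Aim 1, names mixed models in SAS for energy intake by the energy balance method and adds: "Least square means will be compared with the mixed models contrasts". It states no residual variance structure, no variance by gainer class and no degrees-of-freedom method.

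The only spreads by gainer class are in section 2.1: "energy intake in the third trimester was 3503 ± 666 kcal/d compared to 2617 ± 400 kcal/d", High Gainers first. That sentence concerns a different population from the trial's: "In overweight women with gestational weight gain above the 2009 IOM guidelines".

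Section 8.13 builds intake from expenditure plus one change in energy stores between the early and late pregnancy tests. In effect this gives one value per woman for the pregnancy.

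**The concern.** With one value per woman there is no within-woman covariance to model. Unless a variance by group is requested, the mixed model is then an ordinary linear model with one pooled residual variance. Pooling weights each group's variance by its size. If the smaller group is the more variable one, the pooled estimate is pulled towards the less variable group, the standard error of the contrast is too small and the test rejects too often. If the larger group is the more variable one, the error runs the other way.

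The plan's own figures point to the first case: the larger spread is in High Gainers, who are predicted to be the smaller group. There is also a reason to expect the direction. Section 2.1 says "gestational weight gain in obese women should be limited to 5-9 kg", so Normal Gainers lie in a 4 kg band while High Gainers have no upper limit, and stored energy enters the intake value directly. At stake are the p-value and confidence interval of the comparison on which the study was sized.

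**Working it through.** **Inputs.** Two-sided alpha 0.05, SD 700 and group sizes from section 10.1 and Table 4. Spreads of 666 (High) and 400 (Normal) from section 2.1, read as SDs: a ratio of 1.67.

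**Reproducing the plan.** With SD 700 and 17/34, SE = 700 × √(1/17 + 1/34) = 207.9 kcal/d. Two-sample t power is 0.900 at 688 kcal/d and 0.794 at 590, against 0.90 and 0.80 in Table 4. The other four rows also reproduce. (The text under the table pairs 51 women and 590 kcal/d with 90% power, which the table does not. That is a separate matter.)

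**Standard errors at 17 High, 34 Normal.**
- Pooled variance = (16 × 666² + 33 × 400²)/49 = 252,590, so pooled SD = 502.6.
- Pooled SE = 502.6 × √(1/17 + 1/34) = 149.3.
- True SE = √(666²/17 + 400²/34) = √(26,092 + 4,706) = 175.5.
- Ratio = 149.3/175.5 = 0.851, so the pooled SE is 15% too small.

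**Type I error.** The large-sample approximation is 2Φ(−1.96 × pooled SE/true SE) = 2Φ(−1.667) = 9.55%. Simulation with normal data (400,000 draws per setting) gives 9.5% for the pooled test and 5.0% for the unequal-variance (Welch) test.

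**How it depends on the split, SDs 666 and 400.**

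| High/Normal | Pooled test | Welch test |
|---|---|---|
| 17/34 | 9.5% | 5.0% |
| 27/54 | 9.5% | 5.0% |
| 25/26 | 5.4% | 5.0% |
| 30/30 | 5.1% | 5.0% |
| 34/17 | 2.3% | 4.9% |

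At 34/17 the pooled SE is 176.0 against a true 149.9. More women at the same 1:2 ratio do not help.

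**How it depends on the SD ratio, at 17/34.** Pooled type I error is 5.0% at 1.0, 6.9% at 1.25, 8.6% at 1.5 and 11.2% at 2.0.

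**Power cost of separate variances, at 17/34.**
- SDs equal at 700, difference 688: about 90.0% pooled, 89.3% Welch.
- SDs 666 and 400, difference 590: 94.8% pooled, 89.3% Welch.
- SDs 666 and 400, difference 886 (3503 − 2617): above 99% for both.

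**The case against.** A reader might infer that the plan commits to a common variance and that its primary test therefore runs at 9.5%. The documents do not support that. The common SD is a sample-size assumption, and a mixed model can carry separate variances. The gap is silence in section 10.2, which leaves the software default to decide.

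The split is only a prediction. Section 10.1 expects the High Gainer rate to fall from 66% to below 50%, which does not itself imply 1:2. If the rate stayed at 66% the split would be near 2:1 and a pooled test would be conservative. Section 2.1 also reports that more than 55% of obese women exceed the guideline and that earlier interventions failed. This stands, and it means that the direction of the error is unknown.

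The SD ratio is uncertain too. The preliminary women were overweight, not obese. The figures are third-trimester intake with four-compartment body composition, whereas the trial uses MRI and the interval from weeks 13–16 to 35–37. The ± is unlabelled and group sizes are not given.

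The argument from the weight band explains only part of the ratio. Suppose all gain is fat at 9300 kcal/kg (section 8.13), spread over about 150 days. A uniform 4 kg band then has SD 4/√12 = 1.15 kg, or about 71 kcal/d. If the SD of gain among High Gainers were 3 to 6 kg (an assumption, not in the documents), that is 186 to 372 kcal/d. Keeping the Normal Gainer SD at 400, the High Gainer SD becomes √(400² − 71² + 186²) = 435 to √(400² − 71² + 372²) = 541. The ratio is 1.09 to 1.35 and the type I error about 5.7% to 7.6%.

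Finally, at a difference as large as the preliminary 886 kcal/d either test would reject. What is then at stake is the width of the confidence interval.

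**Conclusion.** The point holds as a gap in pre-specification. The 9.5% rests on three conditions together: one residual variance is fitted, SDs near 666 and 400 carry over from overweight to obese women, and the split is about 1:2. If any of them fails, the figure moves towards 5% or, at 2:1, below it. The arithmetic is firm. Confidence in the size for this trial is moderate, and confidence in the remedy is high, because separate variances hold close to 5% at every split examined.

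The planning SD of 700 exceeds both preliminary values. That is conservative for power but does not protect the error rate, which depends on the ratio of the SDs and on the split.

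Two further inferences are tempting and are not supported as errors. One is that the expenditure contrasts in Aim 2 share the problem: the documents give no expenditure SDs by gainer class, and the stored-energy argument does not apply to measured expenditure. The other is that section 10.1 must be reworded: a common 700 is an acceptable planning value, and changing the wording would not change the sample size.

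**What to change.** In section 10.2, Aim 1, state that the model for energy intake by the energy balance method will use residual variances specific to gainer class (in SAS PROC MIXED, a REPEATED statement with GROUP = gainer class) and Satterthwaite or Kenward-Roger degrees of freedom. With one value per woman and no covariates this is the Welch test. The choice should be fixed before gainer class is known, so that it does not depend on the observed split or spreads.

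The cost is one line of model specification, with no new data and no more women. At 17/34 the power loss is under 1 point if the SDs are equal. With the preliminary SDs, power at 590 kcal/d falls from about 95% to 89%, because the pooled test owes its higher figure to its inflated false-positive rate. Applying the same option to Aim 2, or describing 700 kcal/d in section 10.1 as an upper bound for each group, is optional.

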3. RESEARCH DESIGN

This is a single arm, prospective study. In this study, we will enroll up to 75 obese, pregnant women to complete at least 60. This study will be performed at Pennington Biomedical Research Center in Baton Rouge, Louisiana. Study outcomes will be assessed at three time points during pregnancy; namely, gestational weeks 13-16 (early), 24-27 (mid), and 35-37 (late); and at two time points postpartum; namely, postpartum weeks 22-25 and 48-56 (postpartum testing). Infants born to the mothers enrolled in the MomEE study will complete 1 study visit before 10 days of life to measure anthropometrics, body composition measurements, and questionnaires.

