(weeks)	Confirmation of pregnancy-15	13-16	24-27	35-37		+22-25	+48-56
Weight	X	X	X	X		X	X
Height	X						
HbA1c	X						
Prenatal vitamin dispensing/inventory**		X	X	X		X***	
Vital signs (blood pressure, heart rate)	X	X	X	X		X	X
Neck circumference		X	X	X		X	X
Questionnaires	X	X	X	X		X	X
Body composition (BOD POD/SFT)		X	X	X		X	X
Body composition (MRI scan)		X	X	X			X
Energy intake (RFPM)		X		X			X
Accelerometry (Actigraph/Sense Wear)		X		X			X
Doubly Labeled Water (DLW)		X		X			X
Metabolic chamber testing with urine collection		X		X			X
Dinner provided		X		X			X
Breakfast provided		X		X			X
Resting Metabolic Rate (RMR)		X		X			X
Fetal size (3D ultrasound)		X	X	X			
Oral glucose tolerance test							X
Blood collection		X	X	X		X	X
Blood collection for future use*		X	X	X		X	X
Urine collection for future use*		X	X	X		X	X
Placental Biospecimen collection*					X		

*Optional **Subject to participant's needs ***Inventory only

Infant Assessments (Table 2) will be completed at the infant's Delivery visit. The Delivery visit will occur before the infants reach 10 days of life. At the visit, the MomEE participant who is the mother of the infant and signs the minor informed consent will be provided with questionnaires to complete related to the infant. After obtaining written parental informed consent for the infant, weight, recumbent length, head circumference, abdominal circumference and body composition by skinfold thickness and air displacement plethysmography

(PEA POD). Weight, length, and head circumference will be plotted on WHO growth charts. The medical investigator or available nurse practitioner will be called for evaluation of the infant to review any reported adverse events and to determine any signs of jaundice, difficulty breathing, or other obvious congenital malformations. If the medical staff members are unavailable at the time of the visit, follow up may be completed by the medical staff members with the parent/legal guardian of the infant as is deemed necessary. At the MomEE participant mother's 12 month postpartum visit, she will be provided with a Request of Medical Records form to complete for the infant participant so that medical data from the infant's pediatrician's office can be extracted from birth to the end of the infant's first year of life.

Table 2. Infant Assessments	
	Delivery (<10 days old)
Informed Consent (Minor)	X
Length	X
Weight	X
Head Circumference	X
Abdominal Circumference	X
PEAPOD	X
Skinfold Thickness	X
Questionnaires*	X

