8.11. Classification of gestational weight gain

Gestational weight gain will be defined, as recommended by the IOM, as the last measured weight during pregnancy minus the self-reported pre-pregnancy weight [10]. Self-reported pre-pregnancy weight will be validated against chart extracted weights recorded within 6 months of the current pregnancy. If the self-report and the chart extract weight differ too greatly, adjustment of pre-pregnancy weight used will be at the discretion of the principal investigator. The 2009 IOM guidelines for weight gain during pregnancy^[10], will be used to categorize subjects on the basis of gestational weight gain. Subjects with gestational weight gain above the 2009 IOM guidelines (at the time of delivery) will be defined as '*High Gainers*'. Subjects with gestational weight gain within the 2009 IOM guidelines (at the time of delivery) will be defined as '*Normal Gainers*'. Subjects with gestational weight gain below the 2009 IOM guidelines (at the time of delivery) will be defined as '*Low Gainers*' and excluded from the primary analysis.

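### Section 10.1 claims 90% power for 590 kcal/d or 80% for 520 kcal/d with 51 women; its own Table 4 gives 80% for 590 and 90% only for 688

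*Combined protocol and SAP*

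**What the plan says.** Section 10.1 names energy intake during pregnancy as the primary outcome and compares High Gainers with Normal Gainers. It assumes a two-sided test at alpha 0.05, a common SD of 700 kcal/d and a 1:2 ratio of High to Normal Gainers. It also sets a power level: "Our power/sample size analysis (Table 2) assumed: 1) power ≥ 0.90".

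The power table, Table 4, is headed "Minimum sample size for power at .80 and .90, ratio between groups 1:2". Its rows, all at SD 700, are:

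| Groups (total) | Difference at .90 | Difference at .80 |
|---|---|---|
| 27 / 54 (81) | 541 | 468 |
| 22 / 44 (66) | 600 | 520 |
| 17 / 34 (51) | 688 | 590 |

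The sentence that draws on the table begins "As shown in Table 2, with subject assignment to the 2009 IOM guidelines being 1:2" and continues "we require a minimum of 51 subjects, to detect a between group difference of 590 kcal/d with 90% power or 520 kcal/d with 80% power". The section then raises the number to at least 60 completers to cover early deliveries, late MRI scans that cannot be done, and 10% of women gaining less than recommended. Section 8.11 says that these Low Gainers are "excluded from the primary analysis". Section 3 states that "we will enroll up to 75 obese, pregnant women to complete at least 60".

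The table that actually carries the number 2, in section 7, is "Table 2. Infant Assessments".

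**The concern.** The sentence cites the power table and contradicts it. At 51 women the table puts 590 kcal/d at 80% power, not 90%. It has no 520 kcal/d entry at 51 women, and no row pairs 590 with 90%. The sentence also conflicts with the section's own requirement of at least 90% power, which at 51 women the table meets only for 688 kcal/d.

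This is the only power statement for the primary outcome, and it leads directly to the completion target. A reader is likely to carry the sentence forward rather than the table. If it is believed, a non-significant result for Hypothesis 1 would seem to weigh more heavily against a difference of 590 kcal/d than the design allows. The wrong table number makes the conflict harder to notice, because it sends the reader to the infant measurements.

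**Working it through.** **Inputs (section 10.1).** SD 700 kcal/d, two-sided alpha 0.05, ratio 1:2, groups of 17 and 34.

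**Method.** Two-sample t-test with noncentral-t power. SE = SD × √(1/n₁ + 1/n₂), noncentrality = difference / SE, degrees of freedom = n₁ + n₂ − 2.

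**Step 1: reproduce Table 4.**

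| Groups | Difference | Printed power | Recomputed power |
|---|---|---|---|
| 27 / 54 | 541 | .90 | 0.900 |
| 27 / 54 | 468 | .80 | 0.800 |
| 22 / 44 | 600 | .90 | 0.899 |
| 22 / 44 | 520 | .80 | 0.800 |
| 17 / 34 | 688 | .90 | 0.900 |
| 17 / 34 | 590 | .80 | 0.794 |

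All six rows agree with the stated inputs. Solving for the difference at 17/34 gives 594 kcal/d (80%) and 688 kcal/d (90%).

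**Step 2: test the sentence at 17/34.** SE = 700 × √(1/17 + 1/34) = 207.9; 49 degrees of freedom; critical t = 2.010.

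- 590 kcal/d: noncentrality 590 / 207.9 = 2.84, power 79.4% (stated 90%). Chance of missing it: 100 − 79.4 = 20.6%, not 10%.
- 520 kcal/d: noncentrality 520 / 207.9 = 2.50, power 68.9% (stated 80%). Chance of missing it: 100 − 68.9 = 31.1%, not 20%.

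The normal approximation gives 81.0% and 70.6%, so the choice of method does not explain the gap.

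**Step 3: look for a setting in which the sentence is true.**

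| Setting | Power for 590 | Power for 520 |
|---|---|---|
| 60 completers less 10% Low Gainers = 54 (18/36) | 81.7% | 71.4% |
| All 60 evaluable (20/40) | 85.7% | 76.0% |
| All 75 complete, less 10% Low Gainers = 67 (22/45) | 89.1% | 80.3% |
| 51 women, equal groups | 83.9% | 73.9% |
| 17/34, one-sided t-test | 87.6% | 79.4% |

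No setting delivers both stated figures. The one-sided test comes closest, but section 10.1 specifies a two-directional alternative and Table 4 fits two-sided testing.

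**Step 4: what the stated figures would need.** At 1:2 and SD 700, 590 kcal/d at 90% needs 23 + 46 = 69 women (90.2%; 22/44 gives 88.9%). For 520 kcal/d at 80% the requirement is 22 + 44 = 66 (80.0%). With 17/34 fixed, the SD would have to be about 601 for 590 kcal/d at 90% and 612.5 for 520 kcal/d at 80%.

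**Step 5: the preliminary difference.** Section 2.1 reports, for overweight women, that "energy intake in the third trimester was 3503 ± 666 kcal/d compared to 2617 ± 400 kcal/d". The difference is 3503 − 2617 = 886 kcal/d. At SD 700, power is 98.7% with 17/34 and 99.0% with 18/36.

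**The case against.** The strongest reply is that little turns on the error. The correct values are printed in Table 4, in the same section; the preliminary difference is far larger than those in dispute; and power for it is about 99%. All of that stands, and it limits the consequence: the error does not show that the study is underpowered for the effect it expects. That effect came from overweight women, however, and the study enrols obese women, so it cannot stand in for a correct statement of the detectable difference.

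A second reply is that the miss rates depend on an unadjusted t-test and on an SD the plan itself calls conservative, whereas section 10.2 plans mixed models with possible covariates. The section 2.1 SDs of 666 and 400 pool at 17/34 to √[(16 × 666² + 33 × 400²) / 49] ≈ 503, giving about 97% power for 590 and 93% for 520. An unequal-variance test with 666 in the smaller group gives about 89% and 81%. The dependence is real, and the miss rates should be read as conditional on SD 700. But 700 is the SD the sentence and the table both declare, and under it the sentence is wrong.

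A third reply is that the documents do not show which number is mistaken. The sentence resembles the 22/44 row (600 at .90, 520 at .80), so the slip may lie in the 51. That also stands, and the fix allows for it.

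**Conclusion.** The concern holds. Under the plan's own inputs (SD 700 kcal/d, two-sided alpha 0.05, 1:2 split, unadjusted comparison of two means), Table 4 is right and the sentence is wrong in both halves. Power with 51 women is overstated by 90 − 79.4 = 10.6 points for 590 kcal/d and by 80 − 68.9 = 11.1 points for 520 kcal/d. Neither figure is reached with 60 evaluable women.

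Because this is the stated power for the primary outcome, it must be corrected. The error concerns the quoted detectable differences; it does not by itself call the design or the analysis into question. The wrong table number is clerical.

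**What to change.** - Restate the sentence along these lines: as shown in Table 4, 51 evaluable women (17:34) allow detection of about 590 kcal/d with 80% power or 688 kcal/d with 90% power.
- Drop 520 kcal/d, or tie it to 66 evaluable women (22:44).
- Reconcile the requirement of at least 90% power: either give 688 as the 90% figure or say plainly that 590 is at 80%.
- Change both citations of Table 2 in section 10.1 to Table 4.
- Have the sponsor confirm that 51 is the intended minimum. If 590 at 90% or 520 at 80% was the real aim, 69 or 66 evaluable women are needed, and the target of at least 60 completers would have to be reconsidered.

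With 51 kept, the cost is wording in section 10.1 and a less favourable stated power. Enrolment, design and analysis stay as they are.
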